#### 7.2.2.2.4. Maximum Tolerated Dose

The MTD is defined as the highest dose at which  $\leq 1$  of 3 patients or  $\leq 1$  of 6 patients (in an expanded cohort) experience a DLT with IFX-1 in combination with 400 mg pembrolizumab. Thus, the MTD is defined as the dose level immediately below the level at which dosing is stopped due to the occurrence of >1 DLT in a cohort with 3 patients or of >1 DLT in an expanded cohort of 6 patients. If dose escalation is not stopped due to the occurrence of DLTs, it will be considered that the MTD has not been determined and the highest IFX-1 dose level will be considered as dose for Stage 2. 6 patients will need to be treated at the MTD or at the highest IFX-1 dose level (Regimen 3, if MTD was not reached) to decide if this dose can be selected as RP2D which will then be explored in the Phase II portion of Arm B. In case only 3 patients will have been previously treated at the MTD or highest IFX-1 dose level, 3 more patients will be added to this cohort. If 6 patients were already treated at the proposed dose level, then additional patients will not be required and the decision on the RP2D will be made based on the available data.

# 7.2.3. Re-Dosing Criteria

The following criteria must be fulfilled to allow for re-dosing of study treatment:

- Absence of treatment discontinuation criteria (see Section 7.2.4)
- AEs fulfilling DLT criteria (see Section 7.2.2.2.3) must have been reviewed by the steering committee (see Section 5.3.2) and found not to be limiting.
- Any other Grade 3 or higher AEs have to improve to Grade 1 or baseline OR a Grade 3 AE can be managed and stabilized by supportive/medical therapy, e.g., Grade 3 hypertension can be controlled by addition of a second antihypertensive medication and should improve to Grade 1 or baseline.

#### 7.2.4. Treatment Discontinuation Criteria

Discontinuation of study treatment does not represent withdrawal from the study. See Section 5.4.1 for the EOT definition and procedures at EOT Visit.

Patients should be treated with IFX-1 or the IFX-1+pembrolizumab combination until disease progression or unacceptable toxicity occurs or treatment has been administered for approximately 2 years. With Sponsor agreement, drug administration can continue for patients with initial evidence of PD according to RECIST v1.1 (Eisenhower et al., 2009) but are clinical stable in line with the concept of unconfirmed PD (iUPD) according to iRECIST criteria (Seymore et al., 2017).

For the purpose of this decision process, lack of clinical stability is defined as:

- Unacceptable toxicity
- Clinical signs or symptoms indicating clinically significant disease progression
- Decline in performance status

Rapid disease progression or threat to vital organs or critical anatomical sites (eg, CNS metastasis, respiratory failure due to tumor compression, spinal cord compression) requiring urgent alternative medical intervention.

# 7.2.4.1. Monotherapy Arm A

Possible reasons for treatment discontinuation for individual patients are:

- PD/iCPD
- Clinical deterioration
- Non-compliance with protocol procedures
- Study participation consent withdrawal (see Section 5.4.4)
- Pregnancy
- Safety:

- Grade 2 infusion-related reactions despite adequate premedication (see Appendix 8, Table 5)
- Grade 3 or 4 infusion-related reactions (see Appendix 8, Table 5)

# 7.2.4.2. Combination Therapy Arm B

Possible reasons for treatment discontinuation for individual patients are:

- PD/iCPD
- Clinical deterioration
- Non-compliance with protocol procedures
- Study participation consent withdrawal (see Section 5.4.4)
- Pregnancy
- Safety:
  - Any study intervention-related toxicity (immune-related adverse events or infusion-related reactions) specified as a reason for permanent discontinuation as defined in the guidelines for dose modification due to AEs (see Appendix 8, Table 4, Table 5)
- Discontinuation of pembrolizumab treatment may be considered for patients who have attained a confirmed CR and have received ≥2 doses of pembrolizumab beyond the date when the initial CR was declared
- Discontinuation of pembrolizumab treatment may be considered after completion of 18 cycles (approximately 2 years) with pembrolizumab

Upon occurrence of any TEAE that, in the opinion of the investigator, is solely related to either IFX-1 or pembrolizumab, continuation of treatment with the other combination partner alone is possible but requires sponsor agreement. In case of specific IFX-1 toxicities pembrolizumab may be continued as a monotherapy for approximately 2 years.

# 7.3. Premedication and Postmedication

Routine premedication is not required prior to the first dose of IFX-1 or pembrolizumab.

Patients with mild or moderate infusion reaction following IFX-1 or pembrolizumab administration may continue to receive IFX-1 or pembrolizumab with close monitoring; premedication with antipyretic and antihistamine may be considered.

Patients should be observed in the treatment facility for 60 minutes, or longer per clinical judgment, after study treatment administrations.

Treatment guidelines are detailed in Appendix 8, Table 5.

# 7.4. Concomitant Medication/Treatments

Any medication or treatment that the patient is receiving within 28 days prior to the first dose of study treatment and up to 30 days after the last dose should be recorded.

For details, please see Section 8.1.4.

# 7.4.1. Prohibited Concomitant Medication/Treatment

Medications or vaccinations specifically prohibited in the exclusion criteria (see Section 6.2) are not allowed during the ongoing study. If there is a clinical indication for any medication or vaccination specifically prohibited during the study, discontinuation from study therapy or vaccination may be required. The investigator should discuss any questions regarding this with the medical monitor. The final decision on any supportive therapy or vaccination rests with the investigator and/or the patient's primary physician. However, the decision to continue the patient on study treatment requires the mutual agreement of the investigator, the sponsor, and the patient.

The following concomitant therapies or vaccinations are prohibited during the course of the study:

- Antineoplastic systemic chemotherapy or biological therapy
- Immunotherapy not specified in this protocol
- Chemotherapy not specified in this protocol
- Investigational agents other than pembrolizumab and IFX-1
- Radiation therapy
- Note: Radiation therapy to a symptomatic solitary lesion or to the brain may be allowed at the investigator's discretion.
- Live vaccines within 30 days prior to the first dose of study treatment and while participating in the study. Examples of live vaccines include, but are not limited to, the following: measles, mumps, rubella, varicella/zoster, yellow fever, rabies, Bacillus Calmette-Guérin, and typhoid vaccine. Seasonal influenza vaccines for injection are generally killed virus vaccines and are allowed; however, intranasal influenza vaccines (e.g., FluMist®) are live attenuated vaccines and are not allowed. See exclusion criterion #8.
- Systemic glucocorticoids for any purpose other than to modulate symptoms from an AE that is suspected to have an immunologic etiology. The use of physiologic doses of corticosteroids may be approved after consultation with the sponsor.

Note: Inhaled steroids are allowed for management of asthma.

Patients who, in the assessment of the investigator, require the use of any of the aforementioned treatments for clinical management should be removed from the study.

All treatments that the investigator considers necessary for a patient's welfare may be administered at the discretion of the investigator in keeping with the community standards of medical care.

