#### **5.4.1.** End of Treatment Definition

EOT is defined as discontinuation of all study treatment administrations, i.e., IFX-1 alone or in combination with pembrolizumab treatment.

Discontinuation of study treatment does not represent withdrawal from the study.

An EOT Visit will be scheduled 30 days after last study treatment administration or before the patient starts on another antineoplastic therapy, whatever occurs earlier.

A patient, who discontinues study treatment administrations without progressive disease (PD)/confirmed PD (iCPD) will have tumor assessments at follow-up visits until PD/iCPD or start of subsequent antineoplastic therapy.

All patients will be followed for disease progression, survival status, and subsequent antineoplastic therapies as described in Section 5.4.2.

For details on treatment discontinuation criteria, see Section 7.2.4.

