# 5.4.2. Follow-Up

Patients will be followed for survival and subsequent antineoplastic therapies every 3 months for 12 months after the EOT Visit. After the EOT Visit, tumor assessments will continue every 12 weeks until PD/iCPD or initiation of subsequent antineoplastic therapy for patients who discontinued study treatment for other reasons than progression. If required, information can be obtained by a phone call; a follow-up visit can be replaced by a phone call.

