## 10.3.1. Efficacy Analyses

All efficacy analyses will be performed on the FAS. All analyses will be conducted separately by treatment arm. The 2 treatment arms will be compared descriptively. Patients will be analyzed descriptively and stratified by locally advanced or metastatic cSCC.

The primary efficacy variable is the best ORR (investigator assessed) based on modified RECIST v1.1 criteria (Eisenhauer et al., 2009) and iRECIST criteria (Seymore et al., 2017). The number and percentage of responders will be displayed per treatment arm along with its 95% confidence interval according to Clopper-Pearson.

Patients who discontinue the study after assignment to treatment due to 1 of the following reasons will be counted as non-responder if they have not shown response before discontinuation:

- Lack of efficacy
- AE at least possibly related to study treatment
- PD/iCPD
- Clinical deterioration

Statistical inference will be based on the thresholds defined by the Simon's 2-stage design. For decision criteria at the interim analysis, please refer to Section 10.3.4. At the final analysis, the null hypothesis of an ORR of  $\leq$ 5% will be rejected if >3 patients out of a total of 29 patients respond (CR/iCR/PR/iPR). Due to dropouts, the number of patients evaluable for the primary endpoint might not be exactly 29. In this case, appropriate statistical methods will be applied to correct for the deviation from the planned sample size of 29 evaluable patients (Koyama and Chen, 2008). In this case, appropriate statistical methods will be applied to correct for the deviation from the planned sample size of 29 evaluable patients (Koyama and Chen, 2008). Further details will be specified in the SAP.

Additionally, the number and percentage of patients per RECIST tumor response category will be displayed for each scheduled tumor assessment time point.

Secondary Endpoint	Statistical Analysis Methods

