Response (CR/iCR/PR/iPR) duration	Duration of response will be analyzed for patients who reach at least PR/iPR at any time during the study using Kaplan-Meier methods. A responding patient who experiences any form of progression will be evaluated as a patient with event. The starting point is the first diagnosis of CR/iCR or PR/iPR. The time point of the event will be the diagnosis of progression according to RECIST. Responding patients without progression will be censored at their last tumor assessment showing response. Patients who never responded will be excluded from this analysis.
SD duration	Duration of SD will be analyzed using Kaplan-Meier methods. The starting point is the first study treatment administration. A patient who experiences any form of progression will be evaluated as a patient with event. The time point of the event will be the diagnosis of progression according to RECIST (PD) or iRECIST (iCPD). Patients without progression will be censored at their last tumor assessment showing response or any other best overall response except PD/iCPD.
PFS	PFS will be analyzed using Kaplan-Meier methods. A patient who experiences any form of progression or who

	dies of any cause will be evaluated as a patient with event.		
	The time point of the event will be the diagnosis of the		
	first progression according to RECIST/iRECIST or the		
	date of death. Patients without progression and still alive		
	will be censored at their last tumor assessment.		
OS	OS will be analyzed using Kaplan-Meier methods. Death		
	by any cause will be evaluated as event. Patients who are		
	still alive when they discontinue the study will be		
	censored at their last recorded date of being alive.		
Disease control rate	The number and percentage of patients with		
	SD/confirmed SD (iSD) per modified RECIST		
	v1.1/iRECIST or PR/iPR or CR/iCR will be displayed		
	per tumor assessment timepoint.		

Exploratory endpoints will be analyzed descriptively. Further details will be provided in the SAP.

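### Section 7.4.1 takes patients who need a prohibited treatment out of the study, against the plan's own follow-up rules; read literally it censors OS informatively and leaves a narrow gap in ORR

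*Combined protocol and SAP*

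**What the plan says.** **Removal.** After listing the prohibited therapies (anticancer drugs, other immunotherapy, radiation, live vaccines, systemic glucocorticoids, with some exceptions), Section 7.4.1 says that patients who "require the use of any of the aforementioned treatments for clinical management should be removed from the study". The first paragraph of the same section is weaker: it says that "discontinuation from study therapy or vaccination may be required", and it lets study treatment continue if investigator, sponsor and patient agree.

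**Follow-up.** Section 5.4.1 states: "Discontinuation of study treatment does not represent withdrawal from the study". Section 7.2.4 repeats this. Section 5.4.1 adds: "All patients will be followed for disease progression, survival status, and subsequent antineoplastic therapies as described in Section 5.4.2". Section 5.4.2 gives the schedule: "Patients will be followed for survival and subsequent antineoplastic therapies every 3 months for 12 months after the EOT Visit". Section 8.3.8 requires antineoplastic therapy given after study treatment to be recorded until end of study. Section 5.4.3 lists what ends the study for a patient: the last contact of the 12-month follow-up, death, consent withdrawal or loss to follow-up. Need for a prohibited treatment is not on that list.

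**Analysis.** Section 10.2 bases the primary efficacy analysis on the full analysis set (FAS), all patients assigned to treatment, by intention to treat. Section 10.3.1 states: "Patients who discontinue the study after assignment to treatment due to 1 of the following reasons will be counted as non-responder", provided they had not responded earlier. The four reasons are lack of efficacy, an at least possibly related AE, PD/iCPD and clinical deterioration. The section also accepts that the evaluable number may differ from 29. For OS, patients "still alive when they discontinue the study will be" censored at the last date known alive.

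**The concern.** A site that follows the 7.4.1 sentence stops contacting a patient at the moment other treatment becomes necessary. That is when 5.4.2 and 8.3.8 want survival and next therapy recorded. Two endpoints are exposed.

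- **OS (secondary).** Leaving the study triggers censoring. Need for other treatment is plausibly related to prognosis, so the censoring would be informative and the Kaplan-Meier curve too high.
- **ORR (primary efficacy).** Need for a prohibited treatment is not among the four non-responder reasons. A patient who leaves only for that reason, without a response, has no stated status. The wording on evaluable patients leaves room to take that patient out of the denominator.

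Survival data that were never collected cannot be recovered at analysis, so the contradiction is best resolved before it is applied.

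**Working it through.** **1. The passages side by side**

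| Question | 7.4.1, later sentence | Rest of the plan |
|---|---|---|
| What stops? | Study participation | Possibly study therapy only (7.4.1, first paragraph) |
| Does stopping treatment end participation? | Yes, in effect | No (5.4.1, 7.2.4) |
| Survival follow-up afterwards? | None | Every 3 months for 12 months (5.4.2) |
| Later antineoplastic therapy? | Not captured | Recorded to end of study (8.3.8) |
| Is it an end-of-study event? | Implied | Not listed (5.4.3) |

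The two columns cannot both be followed.

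**2. The plan's own design figures (Section 10.1)**

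Inputs: 10 + 19 = 29 patients per arm; stop at 0 responders in stage 1; reject the null at 4 or more in total; p0 = 5%, p1 = 20%.

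- Early termination under p0: 0.95^10 = 0.5987.
- Expected size under p0: 10 + 19 × (1 − 0.5987) = 17.6.
- Rejection probability: sum over x1 from 1 to 10 of P(X1 = x1) × P(X2 ≥ 4 − x1), with X1 ~ Bin(10, p) and X2 ~ Bin(19, p). This is 0.0468 at p = 5% and 0.8011 at p = 20%.

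The stated 59.9%, about 18, 4.7% and 19.9% (1 − 0.8011) are reproduced.

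**3. ORR if such patients are treated as non-evaluable**

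Assumption: m non-responders leave only for a prohibited treatment, are dropped from the denominator and are not replaced. With 4 responders the rate is 4/(29 − m).

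| m | 0 | 1 | 2 | 3 | 4 | 5 | 6 |
|---|---|---|---|---|---|---|---|
| ORR | 13.8% | 14.3% | 14.8% | 15.4% | 16.0% | 16.7% | 17.4% |

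The Clopper-Pearson 95% interval is 3.9% to 31.7% for 4/29 and 4.5% to 36.1% for 4/25.

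The decision rule is hardly touched. If the losses fall in stage 2, a conditional-error adjustment to the attained size keeps the cut-off at 4 responders in total. This holds for every stage 2 size from 19 down to 9, with 1, 2 or 3 responders in stage 1. Dropping non-responders does not change the count of responders, so the trial rejects in the same cases.

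**4. OS if such patients are censored at removal**

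Assumptions, none from the documents: exponential survival with a median of 10 months in patients not removed, λ = ln 2/10 = 0.0693 per month; a share f removed at month 3 with hazard rλ; no other censoring.

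Take f = 20%, r = 2.

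- Full follow-up: with u = exp(−λt), solve 0.8u + 0.2u² = 0.5. Then u = 0.5495 and t = 0.5987/0.0693 = 8.64 months.
- Censored at month 3: S(3) = 0.8 × 0.8123 + 0.2 × 0.6598 = 0.7818. After that only patients not removed are at risk, so t = 3 + ln(0.7818/0.5)/0.0693 = 9.45 months.

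The median is overstated by 0.81 months. By simulation over f = 10% to 30% and r = 1.5 to 3, the overstatement runs from about 0.25 months (9.60 to 9.85) to about 1.4 months (7.06 to 8.47).

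**The case against.** The best defence is that the specific follow-up rules outweigh one loose phrase. Section 5.4.1 schedules the end-of-treatment visit before another antineoplastic therapy starts, so next-line therapy is an expected step into follow-up. Sites would probably keep following these patients. That may be so, but the protocol should not rely on sites choosing the right one of two conflicting instructions.

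Several further points stand and limit the concern:

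- A reader might infer that the plan drops poor-outcome patients from ORR and OS. It does not. For ORR they remain in the FAS, and progression, lack of efficacy and clinical deterioration already count as non-response. At the interim, patients who stopped treatment count toward the 10 (10.3.4.1). For OS they contribute time until censoring.
- A reader might infer an inflated type I error. That would need never-responding patients to be replaced. For example, if 10% were replaced, the null rate among evaluable patients would be 5%/0.9 = 5.6% and the error 6.4%. Section 10.3.1 provides for an adjusted analysis, not for replacement.
- The affected group is smaller than the prohibited list suggests. Section 7.4.1 may allow radiation to a symptomatic solitary lesion or the brain, permits steroids for AEs of suspected immunologic origin, and allows physiologic steroid doses to be approved.
- Tumor assessments end at subsequent antineoplastic therapy in any case (5.4.2), so for those patients that loss is by design.
- The four-reason list also omits consent withdrawal and loss to follow-up. The ORR gap is therefore wider than 7.4.1. Section 10.3 leaves missing-data handling to the SAP, which could close it, but the text available for this review contains no such rule.

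The FAS definition alone does not settle the ORR point. If every FAS patient without a response were automatically a non-responder, neither the four-reason list nor the allowance for fewer evaluable patients would be needed.

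**Conclusion.** The contradiction is certain: it is on the page and does not depend on any assumption. Its consequences are conditional on sites applying 7.4.1 literally.

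For OS the consequence is informative censoring. The 0.25 to 1.4 months rests on assumed removal shares, hazard ratios, removal time and median. For scale, the approximate standard error of a median from 29 exponential survival times at a 10-month median is 1/(λ√29) = 14.43/5.385 = 2.7 months. The bias would be modest beside the noise, but one-directional and avoidable.

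For ORR the gap is narrow. It covers non-responders who leave solely for a prohibited treatment. With an assumed 1 to 6 of them, 13.8% becomes 14.3% to 17.4%. The plan permits that reading without directing it, and without replacement the go/no-go cut-off does not move. The documents give no count for either endpoint.

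**What to change.** 1. **Section 7.4.1.** Reconcile the removal sentence with 5.4.1 to 5.4.3 and with its own first paragraph, so that needing a prohibited treatment does not by itself end study follow-up. Whether study treatment continues is a separate clinical question for the sponsor's rules, and this point takes no position on it.
2. **Section 10.3.1.** State that every FAS patient without a documented response counts as a non-responder, whatever the reason for discontinuation. This also covers consent withdrawal and loss to follow-up. It keeps all 29 in the denominator and preserves the stated 4.7% type I error and 80.1% power.

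The cost is two sentences. Reported ORR may be slightly lower, and there will be some extra follow-up contacts within the 12 months already planned, which 5.4.2 allows by telephone.

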# 7.5. Rescue Medications and Supportive Care

Patients should receive appropriate supportive care measures as deemed necessary by the treating investigator. Suggested supportive care measures for the management of AEs with potential immunologic etiology are outlined along with the dose modification guidelines in Section 7.2.2 and Appendix 8, Table 4. Where appropriate, these guidelines include the use of oral or intravenous treatment with corticosteroids, as well as additional anti-inflammatory agents if symptoms do not improve with administration of corticosteroids. Note that several courses of steroid tapering may be necessary as symptoms may worsen when the steroid dose is decreased. For each disorder, attempts should be made to rule out other causes such as metastatic disease or bacterial or viral infection, which might require additional supportive care. The treatment guidelines are intended to be applied when the investigator determines the events to be related to pembrolizumab.

Note: If after the evaluation of the event, it is determined not to be related to pembrolizumab, the investigator does not need to follow the treatment guidance.

It may be necessary to perform conditional procedures such as bronchoscopy, endoscopy, or skin photography as part of evaluation of the event.

